5.2.1 Exclusion of Special Populations

Children: Children <3 years old will be excluded from enrollment in this study because this population is not typically seen at NIAID.

Non-English speakers: Because this study will use questionnaires that are not validated in languages other than English, individuals who are not fluent in English will be excluded from enrollment.

5.3 Inclusion of Vulnerable Participants

Children: As the immune deficiencies and dysregulations being studied under this protocol affect all age ranges, information gathered from all eligible children (both affected and control participants) will be important for providing a full understanding of any potential differential effects across age ranges. Children will only be enrolled if there is FDA authorization or approval for use of a COVID-19 vaccine in that age group.

Adult subjects who lack capacity to consent to research participation: Individuals who are unable to provide initial informed consent are excluded from the study. If participants lose the ability to provide ongoing consent subsequent to giving initial consent, they will be withdrawn from the study.

NIH staff or family members of study team members: NIH staff and family members of study team members may be enrolled in this study if they meet the study entry criteria. Neither participation nor refusal to participate in the research will have an effect, either beneficial or adverse, on an individual's employment or position at NIH.

Every effort will be made to protect subject information, but such information may be available in medical records and may be available to authorized users outside of the study team in both an identifiable and unidentifiable manner.

The NIH investigator will provide and request that the NIH staff member review the Frequently Asked Questions (FAQs) for Staff Who are Considering Participation in NIH Research and the Leave Policy for NIH Employees Participating in NIH Medical Research Studies (NIH Policy Manual 2300-630-3). Please see section 9.1.2 for consent of staff members.

5.4 Inclusion of Pregnant Women, Fetuses, or Neonates

As accumulating data indicate that the vaccines are safe and effective in pregnant people, this protocol will allow the enrollment of this population to allow evaluation of the immune response to COVID-19 vaccines in pregnant people with immune disorders, which may differ from the response in non-pregnant people.

5.5 Lifestyle Considerations

Not applicable.

5.6 Screen Failures

Screen failures are defined as participants who consent to participate in the clinical study but are not subsequently entered in the study. Individuals who do not meet the criteria for participation in this study (screen failure) may be rescreened if they turn 12 before the study enrollment closes and have not yet received a COVID-19 vaccination, if the participant's time since non-COVID-

19 vaccination has passed 14 days and they remain unvaccinated for COVID-19, or their medical status changes such that the PI feels exclusion is no longer necessary.

5.7 Strategies for Recruitment and Retention

Immunodeficient individuals will be recruited from NIAID protocols that evaluate primary or secondary immune deficiencies. Potential subjects will be identified by discussion between the study teams and review of medical and research records if necessary. They may also be referred from community practitioners who see this population.

Healthy adult volunteers will be recruited through the NIH Clinical Research Volunteer Program, the Office of Patient Recruitment, MMG Patient Recruitment, ResearchMatch, or BuildClinical. Volunteers will also be recruited from existing NIH protocols, including but not limited to protocol 18-I-0101 (“Sample Collection From Healthy Volunteers For Assay Optimization”), 93-I-0119 (“Detection and Characterization of Host Defense Defects”), 18-I-0041 (“Investigating the Mechanistic Biology of Primary Immunodeficiency Disorders”), 11-I-0187 (“Natural History of Individuals with Immune System Problems that Lead to Fungal Infections”), and 17-I-0122 (“NIAID Centralized Sequencing Protocol”). Healthy relatives of immunodeficient participants can be recruited for participation as controls if they meet enrollment criteria.

An IRB-approved recruitment email will be distributed to potential participants, and flyers with study team contact information will be posted throughout the CC and provided to community practitioners to share with potentially eligible patients. We may also conduct outreach activities with local groups involving patients with immune deficiencies (eg, support groups and patient advocacy groups). Interested individuals may also contact the study team directly via email.

A pre-screening phone call will be conducted with individuals who express interest, for an initial discussion of eligibility (including any past SARS-CoV-2 testing) and scheduling prior to the screening visit.

5.7.1 Costs

There will be no costs to participants for procedures performed at the NIH CC. Similarly, participants will not incur costs for blood drawn at Quest laboratories, as Quest will be paid directly through a contract set up for this purpose. Participants may incur costs of blood draws performed at off-site facilities other than Quest laboratories; in this case, they will be reimbursed up to \$85 for each blood draw.

5.7.2 Compensation

Compensation will be dependent on the sample collections and study visits that a subject participates in. Participants will be compensated maximum amounts as follows:

- \$10/off-site microsampler or \$20/off-site venous blood x up to 6 timepoints
- \$50/on-site venous blood x up to 10 timepoints
- \$10/on time x up to 2 timepoints (for on-time completion of follow-up at 14-21 or 21-28 days after each vaccination)
- \$10 bonus (for completing all sample collections)
- \$5/saliva x 13 timepoints

Participants may receive a total maximum compensation of \$595 for participating in all possible on-site sample collections and visits. If participants participate in additional visits following booster vaccination(s), they will be compensated for each additional visit/sample collection according to the amounts listed above.

6 PARTICIPANT DISCONTINUATION/WITHDRAWAL

6.1 Participant discontinuation/withdrawal from the study

Participants are free to withdraw from participation in the study at any time upon request. An investigator may discontinue or withdraw a participant from the study for the following reasons:

- Refusal to submit blood samples for testing
- If the participant meets an exclusion criterion (either newly developed or not previously recognized) that precludes further study participation
- Screen failure

The reason for participant discontinuation or withdrawal from the study will be recorded.

6.2 Lost to follow-up

A participant will be considered lost to follow-up if they fail to provide required post-vaccine blood samples and are unable to be contacted by the study site staff.

The following actions will be taken if a participant fails to return required study samples:

- A study staff member will attempt to contact the participant and reschedule the missed sample within the allowable window if possible, counsel the participant on the importance of maintaining the assigned sample schedule and ascertain if the participant wishes to and/or should continue in the study.
- Before a participant is deemed lost to follow-up, the investigator or designee will make a reasonable effort to regain contact with the participant (where possible, 3 telephone calls). These contact attempts should be documented in the participant's medical record or study file.
- Should the participant continue to be unreachable, he or she will be considered to have withdrawn from the study with a primary reason of lost to follow-up.

All samples and data received prior to a subject dropping out or being lost to follow-up will be analyzed unless the participant explicitly requests their data not be included.

7 STUDY ASSESSMENTS AND PROCEDURES

The following study assessments and procedures will be performed according to the schedule provided in section 1.2.

7.1 Screening procedures

7.1.1 Screening activities performed prior to obtaining informed consent

Minimal risk activities that may be performed before the subject has signed a consent include the following:

- Email, written, in-person, or telephone communications with prospective subjects.

- Review of the NIH CC patient medical records (if applicable).

7.1.2 Screening activities performed after obtaining informed consent

After the subject signs the consent form, eligibility will be confirmed and the baseline study procedures will continue.

7.2 Clinical Evaluations

Medical and medication history: Subjects enrolled on a protocol at NIAID will have their clinical history extracted from the NIH Clinical Research Information System (CRIS) for complete review of medical and medication history, including review of vaccination history and SARS-CoV-2 testing and symptom history. The questionnaire (described below) will also elicit information about relevant medical history, including history of SARS-CoV-2 infection. Subjects not enrolled on another NIAID protocol will undergo standard medical and medication history review by questioning.

Venous blood draw: Blood will be collected by venipuncture for laboratory testing (section 1.2) and storage. If participants cannot be brought to the NIH CC due to the ongoing COVID-19 pandemic, individuals can choose to have blood drawn at a primary care provider, academic hospital laboratory, Quest Diagnostics, or through collaboration with the Immune Deficiency Foundation, as necessary. Samples collected at clinics or at Quest may be labeled with a coded identifier, gender, and date of birth, as required by the local facility. The amount of blood drawn for research purposes in pediatric subjects will not exceed 5 mL/kg in a single day or 9.5 mL/kg over any eight-week period, in accordance with the CC Medical Administrative Series Policy M95-9 Guidelines for Limits of Blood Drawn for Research Purposes in the Clinical Center. The amount of blood drawn from pregnant participants will not exceed 50 mL over any eight-week period.

Fingerstick blood collection: All participants will be provided with a microsampler kit and mailing supplies to collect an at-home blood sample by fingerstick and send it to the CC. The sample will be used for laboratory testing (section 1.2) and storage.

Saliva collection: All participants will be provided with saliva collection kits and mailing supplies to collect post-vaccination saliva samples to return to the CC.

Electronic questionnaires: Five separate Research Electronic Data Capture system (REDCap) questionnaires will be completed electronically in REDCap by subjects and/or their parents/guardians throughout the study. A link to the questionnaires will be sent to the personal email address on file. The baseline questionnaire will capture medical history, and any COVID-19 symptoms, severity, and treatment the participant may have experienced. The follow-up questionnaires will assess changes in health history or medications and AEs following study vaccination. An optional survey will ask participants about their beliefs and behaviors around COVID-19 vaccinations, and whether they have changed since before the primary vaccine series and/or booster doses. The questionnaires and their timing are listed below:

1. Baseline medical history and screening questionnaire (Baseline)
2. COVID-19 baseline/post-vaccine infection symptom questionnaire (Baseline and following COVID-19 infection)
3. Changes in medical history questionnaire (Following sample collection)
4. Post-vaccine adverse events questionnaire (Following vaccination)

5. COVID-19 Attitudes and Behaviors Survey (Following primary series and/or booster)

AE assessment: Only AEs related to study procedures (blood draw, fingerstick, and saliva collection) will be followed. COVID-19 vaccines are not administered as study procedures under this protocol; therefore, while we are interested in collecting AEs related to vaccination in our study population, these are not considered study-related events and will not be followed as such. Subjects will be assessed for AEs at each study visit. Information on AEs related to the study procedures that develop within 2 days after the procedure will be collected by participant report and followed through resolution or until the site investigator judges that the event has stabilized and no additional follow-up is required.

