1.2 Schedule of Activities

Evaluation	Study Day (window)							
	Screening and Baseline*	Vaccine dose 1 Follow-up			Vaccine dose 2 Follow-up [‡]			Optional Follow-up [†]
	-7 to 0	1 day after vaccination [§]	3 days after vaccination [§]	14-21 OR 21-28 days after vaccination ^{**}	1 day after vaccination [§]	3 days after vaccination [§]	21-28 days after vaccination ^{**}	6, 12, and 24 months (±2 weeks) after last vaccination
Informed consent	X							
Clinical Procedures and Evaluations								
COVID-19 history and symptom questionnaire	X							
Baseline medical history and screening questionnaire	X							
Changes in medical history questionnaire				X			X	X
Electronic AE questionnaire [^]				X			X	
Behavioral questionnaire							X	
Clinical Laboratory Evaluations ^{^^}								
Blood Volume (mL)								
CBC with differential	3 mL	4 mL	4 mL	3 mL	4 mL	4 mL	3 mL	
TBNK lymphocyte phenotyping/flow/cytok		[X]	[X]		[X]	[X]		

Research Laboratory Evaluations ^{^^}	Blood Volume (mL)							
	0.8 mL	0.8 mL	0.8 mL	0.8 mL	0.8 mL	0.8 mL	0.8 mL	0.8 mL
Mitra microsampler [¶] 
 SARS-CoV-2 antibody (S, RBD, N – IgG, IgM, IgA) Autoantibodies 	0.8 mL			0.8 mL			0.8 mL	0.8 mL
Serum (red cap) ^{††} 
 Neutralizing SARS-CoV-2 antibodies 	5 mL	5 mL	5 mL	5 mL	5 mL	5 mL	5 mL	5 mL
Plasma isolation (EDTA purple cap) [¶] 
 DNA isolation (for high throughput sequencing of TCR/BCR repertoire and for genetic studies) 	10 mL	10 mL	10 mL	10 mL	10 mL	10 mL	10 mL	10 mL
PAXgene tube ^{††} 
 Whole blood RNA 	2.5 mL	2.5 mL	2.5 mL	2.5 mL	2.5 mL	2.5 mL	2.5 mL	2.5 mL
PBMC isolation (sodium heparin green top OR EDTA purple cap) ^{††} 
 Lymphocyte/plasmablast Functional T cells 	10 mL	10 mL	10 mL	10 mL	10 mL	10 mL	10 mL	10 mL
Saliva ^{‡‡} 
 SARS-CoV-2 PCR and sequencing 	Bi-weekly through 6 months							
Daily Blood Volume	31.3 mL	31.5 mL	31.5 mL	31.3 mL	31.5 mL	31.5 mL	31.3 mL	31.3 mL
Cumulative Blood Volume	31.3 mL	62.8 mL	94.3 mL	125.6 mL	157.1 mL	188.6 mL	219.9 mL	251.2 mL (6 mos.) 282.5 mL (12 mos.) 313.8 mL (24 mos.)

[X] = will be performed with portion of sample collected for CBC with differential and does not require additional volume.

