Abbreviations: AE, adverse event; BCR, B cell receptor; CBC, complete blood count; COVID-19, coronavirus disease 2019; DNA, deoxyribonucleic acid; EDTA, ethylenediaminetetraacetic acid; Ig, immunoglobulin; PBMC, peripheral blood mononuclear cell; N, nucleocapsid; RBD, receptor binding domain; RNA, ribonucleic acid; S, spike; SARS-CoV-2, severe acute respiratory syndrome coronavirus 2; TBNK, T, B, and natural killer (cells); TCR, T cell receptor; NP, nasopharyngeal; OP, oropharyngeal; PCR, polymerase chain reaction.

*Baseline sampling and questionnaire can happen on the day of vaccination as long as it is prior to receiving the dose. Participants may enroll after vaccination was already performed. If these individuals do not have current plans for an additional booster dose, previous timepoint samples will not be obtained and they will proceed with the next relevant sampling timepoint. In this situation, if stored blood samples from studies in which subjects are concurrently enrolled are available, they will be used. If stored samples are not available, these samples will be considered waived. If these individuals plan to receive an additional booster vaccination(s), they will be enrolled prior to the booster dose and follow the normal schedule, including a baseline draw prior to the booster.

**The exact timing of these visits will depend upon vaccine manufacturer and platform (as detailed in the Manual of Procedures) but will fall within the ranges indicated. For subjects who decline participation in the optional long-term follow-up visits, study completion will end after the dose 1 or 2 follow-up visit(s), depending on whether the subject received a 1-dose or 2-dose vaccine. Each time a participant receives an additional booster dose while they are still on study, a 21-28-day visit will be performed, and optional long-term follow-up visits will be offered. Samples will be requested from participants as scheduled after each vaccination and booster (+/- 7 days) however samples received outside of the requested windows are acceptable and will be analyzed at the discretion of the PI.

‡ Not all vaccines require a second dose and therefore these follow-up timepoints will be not applicable for participants receiving those vaccines.

^AE questionnaire will be administered after any additional booster dose.

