Additional research evaluations include analysis of the nature, diversity, and frequency of SARS-CoV-2 specific T- and B-cell receptor clonotypes. These evaluations will be used to assess pre-vaccination SARS-CoV-2 exposure and expected response to vaccination. Additional research evaluations may include virus neutralization assays to assess antibody functional response, flow cytometry, and transcriptome and genetic analyses. Comparisons of the immune response will be made among immunodeficiency/dysregulation subtypes and against healthy controls. This will allow characterization of the differences in post-vaccination immune responses and AE presentation.

Subjects will be asked at baseline about prior COVID-19 diagnosis, symptoms, and severity using standardized questionnaires. This will allow us to characterize the different manifestations of COVID-19, potentially including a lack of hyper-inflammatory symptoms associated with severe disease due to dysregulation of the immune response that will be present in many of the study participants. To conduct active screening for post-vaccination COVID-19 infections, participants will be sent optional saliva collection kits to return to the NIH bi-weekly for 6 months, for PCR and genetic sequencing of the virus. Participants whose samples are PCR positive will be asked to submit an additional COVID-19 symptom questionnaire and will be referred for care as needed. Each time a participant receives an additional booster dose while they are still on study (through the 5th COVID-19 vaccine a person receives), they may participate in optional bi-weekly saliva collections for an additional 6-month period. Since this is optional, saliva samples received outside of the requested windows are acceptable and will be analyzed at the discretion of the PI. At follow-up timepoints, participants will be asked about all possible vaccine-related AEs, which will be particularly important given recent information about possible vaccine-induced anaphylaxis.

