8.4.2 Analysis of the Secondary Endpoints

We will calculate descriptive summaries, stratified by immune deficiency/dysregulation group, for incidence of vaccine-associated AEs listed in the Post-Vaccine Adverse Events questionnaire. Incidence of AEs among immune deficient/dysregulated patients will be compared with incidence among healthy volunteers using regression analyses, possibly adjusting for covariates, such as age and sex, as deemed appropriate.

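### No pre-dose symptom report matching the vaccine AE questionnaire is scheduled, so background symptoms can inflate AE incidence in affected participants relative to healthy volunteers

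*Combined protocol and SAP*

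**What the plan says.** The secondary objective (section 3) is to characterize vaccine-associated AEs in people with immune deficiency or dysregulation against healthy volunteers.

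- **Timing of the form.** Section 7.2 lists "Post-vaccine adverse events questionnaire (Following vaccination". In section 1.2 the row "Electronic AE questionnaire" is marked at the post-dose-1 and post-dose-2 follow-up visits and not at baseline. A footnote adds that the "AE questionnaire will be administered after any additional booster dose". No pre-booster form is mentioned.
- **Baseline data.** Section 1.2 schedules a medical history and screening questionnaire and a "COVID-19 history and symptom questionnaire". Section 7.2 describes their content: "The baseline questionnaire will capture medical history, and any COVID-19 symptoms, severity, and treatment the participant may have experienced".
- **What is asked after the dose.** Section 4.1 says "participants will be asked about all possible vaccine-related AEs". The documents do not show the form, its recall window or any attribution rule.
- **Analysis.** Section 8.4.2 says "Incidence of AEs among immune deficient/dysregulated patients will be compared with incidence among healthy volunteers using regression analyses", with optional covariate adjustment for which age and sex are the examples.
- **Groups.** Section 5.1 requires controls to have no evidence of immune deficiency or dysregulation. Section 8.2 makes them representative of the affected participants by age bin and sex only.

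**The concern.** The affected groups in section 8.2 include autoinflammatory disorders, immune dysregulation, combined immunodeficiency and transplant recipients. It is reasonable to expect, though the documents give no rates, that such people have more fever, fatigue, rash or joint pain in an ordinary few weeks than healthy volunteers have. If so, the volunteers do not show what affected participants would have reported without a vaccine. A difference in reported AEs could then appear with no difference in vaccine effect, and balance on age and sex would not remove it.

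The primary endpoint is protected against this. Titers are sampled before the dose, and section 8.4.1 models them with a timepoint-by-baseline interaction. The AE endpoint has no counterpart. Sections 2.1 and 2.2 give the lack of safety data in people excluded from vaccine trials as a reason for the study, so a spurious excess would mislead the population it is meant to inform. A matched symptom report that was not collected before the dose cannot be reliably reconstructed later.

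**Working it through.** The plan states no rate, power or sample size for the AE comparison, so there is no figure to reproduce. What follows illustrates how the size of the bias behaves.

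**Inputs**
- Group sizes: 400 affected and 100 volunteers (section 1.1; section 8.2 gives 120 volunteers). Subgroup of 40: predominantly antibody deficiencies (section 8.2).
- Two-sided 5% level: stated in section 8.3 for titers only and borrowed here.
- Assumed, not in the documents: background risk b over the recall window of 5% in volunteers and 20% in affected participants (range 10% to 30%); vaccine-caused risk v equal in both groups; the two independent; every background symptom reported as an AE.

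**Formula.** P(report) = 1 − (1 − b)(1 − v). The false difference is therefore (1 − v)(b_affected − b_volunteer).

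For v = 5%: volunteers 1 − 0.95 × 0.95 = 9.75%; affected 1 − 0.80 × 0.95 = 24.0%. The difference is 0.95 × 15 = 14.25 points.

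The last two columns give the chance of a significant excess in affected participants (normal approximation for two proportions). With equal background rates that chance is 2.5%.

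| v | Volunteers | Affected | False difference (points) | Risk ratio | 400 vs 100 | 40 vs 100 |
|---|---|---|---|---|---|---|
| 5% | 9.75% | 24.0% | 14.25 | 2.46 | 93% | 59% |
| 10% | 14.5% | 28.0% | 13.5 | 1.93 | 83% | 47% |
| 30% | 33.5% | 44.0% | 10.5 | 1.31 | 48% | 22% |
| 50% | 52.5% | 60.0% | 7.5 | 1.14 | 28% | 12% |
| 70% | 71.5% | 76.0% | 4.5 | 1.06 | 16% | 7% |

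**Range.** At v = 5%, affected background of 10% gives 14.5% (ratio 1.49) and 30% gives 33.5% (ratio 3.44), against 9.75% in volunteers.

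**Would a new-or-worse definition be enough?** Take a yes/no symptom and the same 5% and 20% backgrounds.
- Persistent background: a new event has probability (1 − b)v. At v = 40% this is 0.95 × 0.40 = 38% in volunteers and 0.80 × 0.40 = 32% in affected participants. Masking produces a false deficit of 6 points.
- Episodic background, independent between periods: (1 − b)[1 − (1 − b)(1 − v)]. At v = 5% this is 0.95 × 0.0975 = 9.3% and 0.80 × 0.24 = 19.2%, a ratio of about 2.1. Most of the bias remains.

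**Does a pre-to-post contrast work?** It depends on the scale.
- Ratio of not reporting, post to pre: (1 − b)(1 − v)/(1 − b) = 1 − v in both groups. At v = 5%: 0.9025/0.95 = 0.95 and 0.76/0.80 = 0.95. There is no false difference, whether background is persistent or episodic.
- Difference in risk, at v = 40%: 43 − 5 = 38 points and 52 − 20 = 32 points. The false deficit returns.
- Odds ratio, at v = 40%: (0.43/0.57)/(0.05/0.95) = 14.3 and (0.52/0.48)/(0.20/0.80) = 4.3. A default logistic group-by-period term would show a large false difference.

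**The case against.** The strongest reply is that the bias rests on a form nobody outside the study can see. Its items, recall window and attribution wording are not reproduced, and the text speaks throughout of AEs linked to vaccination. A form limited to the first days after a dose, or one asking only for new symptoms, would let in much less background. This stands. A reader might infer that background symptoms are counted as vaccine AEs by rule, or that the form covers three to four weeks because of when it is given. The documents support neither; they show a risk of misattribution.

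A reader might also infer that nothing about symptoms is recorded before the dose, or that section 8.4.2 compares unadjusted incidence. Both go too far. Baseline medical history and COVID-19 symptom questionnaires exist, section 7.2 provides for chart extraction or history-taking, and a changes-in-history form accompanies the post-dose AE form. Section 8.4.2 specifies regression, and age and sex are only examples of covariates. None of these sources, however, is described as the AE item list over a comparable recent period, and section 8.4.2 does not say that any of them will enter the AE analysis.

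Nor does the statement that vaccine AEs are "these are not considered study-related events and will not be followed as such" settle attribution. It explains that externally given vaccines are not study procedures.

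Finally, the study is exploratory and the endpoint secondary, with no stated alpha or power. That lowers the urgency. It does not remove the bias, which does not shrink as numbers grow.

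**Conclusion.** The point holds in a limited form, as a cheap improvement. The documents establish that the AE form is post-dose only, that no matching pre-dose report is scheduled, and that the AE analysis names no use of baseline symptoms. It follows that a difference in background symptoms between the groups can appear as a difference in vaccine-associated AEs, unless the form fully separates new from pre-existing symptoms.

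The size cannot be computed from the documents. Under the stated assumptions it is modest for very common reactions (4.5 points, ratio 1.06, at v = 70%) and large in relative terms for uncommon ones (14.25 points, ratio 2.46, at v = 5%). The direction, towards more AEs in affected participants, assumes that they have the higher background. The illustration also assumes equal vaccine effect, independence, and full reporting of background symptoms as AEs. If the form filters some of them out, the bias is smaller.

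**What to change.** 1. Add the AE form's symptom items and severity scale to the existing baseline REDCap form. It should be completed before the dose, or before the booster for those enrolled pre-booster, with a recall period equal to that of the post-dose form.
2. In section 8.4.2, make the main AE contrast the between-group comparison of pre-to-post change: a group-by-period term in a repeated-measures regression. Fix the scale in advance, for example the ratio of not reporting the symptom (log link on non-reporting), since risk-difference and odds-ratio scales can create a false difference.
3. Give new-or-worse-than-pre-dose incidence as a supportive summary only, because it can mask events or leave bias.
4. Keep post-dose incidence for all participants as a descriptive summary, and report those without a pre-dose form separately.
5. State the AE form's recall window and attribution wording in the plan.

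Cost: one block in an existing electronic form, a few minutes per participant, and a revised analysis paragraph. People enrolled after vaccination, whose number the documents do not give, will not contribute to the change contrast.
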